## REVISION HISTORY

Revision #	Version Date	Summary of Changes	Consent Change?
01	08-27-2019	Updated Primary investigator and student investigator, Changed VAS to NRS to reflect the correct name of the scale being used, changed sample size, changed procedures involved to reflect multiple appointments and timing of pain assessment, updated inclusion criteria	yes
02	10-3-2019	Updated student investigator to add [name]. Minor changes to study design, primary objective, sample size, duration of appointments to reflect collecting data from only symptomatic patients.	

NOTE: Leave this section blank for the initial submission. The revision history should be documented for modifications to approved studies.

## **ABBREVIATIONS/DEFINITIONS**

- AED: Automated External Defibrillator
- AHC-IS: Academic Health Center – Information Systems
- Ca(OH)2: Calcium Hydroxide
- CBCT: Cone Beam Computed Topography
- EDTA: Ethylenediaminetetraacetic Acid
- NaOCl: Sodium Hypochlorite
- VAS: Visual Analog Scale
- NRS: Numeric Rating Scale

**STUDY SUMMARY**

Study Title	Post-operative pain following treatment using the Gentlewave system
Study Design	Confirmation of pre-operative pain (symptomatic status) will be determined by having the patient record their pain level to percussion at the initial examination using the NRS scale. Additionally, the force required to cause pre-operative pain to biting will be recorded using a digital occlusal force meter. The NRS will consist of a 100mm line where 0 equals 'no pain' and 100 equals the 'worst pain imaginable'. Patients will be divided into one of two treatment groups: 1) standard root canal cleaning and shaping procedures (control group) or 2) the Gentlewave technique, which uses sonic energy and irrigation for cleaning of the root canal system (research group). Patient demographics, anesthesia, cleaning and shaping instruments, irrigation technique, and obturation method and material will be recorded, along with the number of appointments, detailed notes of treatment rendered, and the occurrence of over-instrumentation or overfill of obturation material. Following the first and final appointment, patients will be given the same NRS to take home and record their level of pain at 6, 24, 72, and 168 hours post-treatment.
Primary Objective	To determine whether treatment with the Gentlewave system will significantly decrease the occurrence and of post-operative pain in symptomatic patients following endodontic treatment.
Secondary Objective(s)	If post-operative discomfort should occur, to determine the severity based on an NRS for pain assessment.
Research Intervention(s)/ Investigational Agents	Gentlewave system for root canal disinfection
Scientific Assessment	Not required, Minimal Risk Study
IND/IDE # (if applicable)	N/A
IND/IDE Holder	N/A

Investigational Drug Services # (if applicable)	N/A
Study Population	The target population of the study includes patients needing endodontic treatment in the University of Minnesota Graduate Endodontics clinic, ages 18+. Patients with teeth that have root apices in the maxillary sinus, teeth with immature root apices, and teeth with insufficient coronal tooth structure will be excluded.
Local Sample Size (number of participants recruited locally)	Approximately 150 participants will be recruited. [name] original study was approved for 50 pts, our study will break symptomatic patients into 1 of 2 symptomatic categories: necrotic or vital pulps. So 50 participants in each group, 100 total new patients will be recruited.

## 1. Objectives

1.1. Purpose: *The purpose of this study is to determine whether a new treatment modality for cleaning and disinfecting the root canal system will significantly affect the occurrence and severity of post-operative pain in symptomatic patients.*

## 2. Background

2.1. Significance of Research Question/Purpose: To further the scientific discussion and recognize treatment modalities that may eliminate the occurrence of post-operative pain.

2.2. Preliminary Data: N/A

2.3. Existing Literature: Once a tooth reaches a level of inflammation where healing can no longer occur or when the pulp space begins to go through necrosis, root canal treatment is indicated. The goal of root canal therapy is to clean, shape, disinfect, and obturate all canal systems within the tooth. Schilder's mechanical and biological objectives for cleaning and shaping includes: preparing a continuous tapering root canal funnel from access to apex, cross-sectional diameters should be wider at every point as you move coronally, the preparation should occupy as many planes as presented by the original canal and should follow the shape of the original canal, the apical foramen should remain in its original spatial relationship to bone and to root surface, the apical opening should be kept as small as practical in all cases, complete cleaning and shaping in one appointment, procedures should be confined to the roots themselves, necrotic debris should not be forced

beyond the foramina, all tissues should be removed from root canal space, and sufficient space for intracanal medicaments and irrigation should be created (1). Peters added to these objectives in creating his own basic objectives for cleaning and shaping that include: removing infected soft and hard tissue, giving disinfecting irrigants access to the apical canal space, creating space for the delivery of intracanal medicaments and subsequent obturation, and retaining the integrity of radicular structures (2).

Traditionally, the standard protocol for cleaning and shaping is completed using hand or rotary files. Various file systems are used to prepare root canal systems to the parameters set by Schilder's and Peters' principles. In addition, it is important to keep necrotic debris within the canal space as a means of preventing post-operative pain and flare-ups (3). Siqueira discovered that the factors that are commonly responsible for post-operative or interappointment pain include mechanical preparation and obturation beyond the apex, bacterial insults not present in the primary infection, and chemical extrusion of irrigant materials beyond the apex (3). Post-operative pain can occur hours to days following root canal procedures. Acute inflammation due to the aforementioned etiologic factors is the chief cause of post-operative pain. According to Gotler et al, post-operative pain typically occurs at a higher severity and incidence in vital teeth and retreatments as opposed to non-vital teeth (4). Irrigation dissolves organic material and kills microbes. It also helps prevent the binding of instruments, improves the cutting effectiveness of files, dissolves tissue, and cools the instrument and tooth (5). The most common endodontic irrigant is sodium hypochlorite (6). Sodium hypochlorite is an alkaline fluid with a pH of approximately 11-12. It hydrolyzes proteins and causes hemolysis of red blood cells which leads to the dissolution of vital, as well as necrotic tissue. Upon contact of organic debris, hypochlorous acid forms which disrupts bacterial metabolism by oxidizing the sulphydryl group of bacterial enzymes. With the use of such a caustic material, there is always the possibility of complications. Most hypochlorite accidents occur because of inaccurate working length determination, iatrogenic widening of the apical foramen, lateral perforation, or wedging of the irrigation needle. Once irrigant is extruded beyond the apex, severe pain, uncontrollable bleeding, immediate swelling, and bone and tissue necrosis can occur (7&8). Standard endodontic treatment protocol includes irrigation with 5.25% sodium hypochlorite between each file used for cleaning and shaping with a final ultrasonic activation of the sodium hypochlorite for 30 seconds per canal. Lastly, there is a one minute soak of 17% EDTA to remove the layer of debris created from cleaning and shaping (5).

### **3. Study Endpoints/Events/Outcomes**

- 3.1. Primary Endpoint/Event/Outcome: The primary outcome of this study is to determine whether treatment with the Gentlewave system will significantly decrease the occurrence of post-operative pain with endodontic treatment.
- 3.2. Secondary Endpoint(s)/Event(s)/Outcome(s): The secondary outcome is to determine the intensity of pain, should it occur, based on a NRS pain assessment.

#### **4. Study Intervention(s)/Investigational Agent(s)**

- 4.1. Description: The Gentlewave system is a FDA cleared root canal irrigation device that uses internally degassed distilled water, 3% NaOCl, and 8% EDTA to allow for a more thorough cleaning within the tooth (8). The system uses broad spectrum acoustic energy to create hydrodynamic cavitation and thousands of micro bubbles that create powerful shear forces. The fluids work to remove necrotic tissue, debris, biofilm, and bacteria while leaving dentin intact and preserving tooth structure. The cleaning and shaping protocol when using the Gentlewave system requires the clinician to prepare all canals within a tooth to a minimum of size 20 before using the Gentlewave system for irrigation. The Gentlewave irrigation replaces the NaOCl ultrasonic activation and EDTA steps of the standard endodontic protocol. Use of the Gentlewave system is contraindicated in teeth with immature apices, teeth with insufficient coronal structure, and teeth with root apices extending into the maxillary sinus.
- 4.2. Drug/Device Handling: The Gentlewave device will be stored in the Graduate Endodontics research laboratory and any treatment fluids specifically for research purposes will be locked and labeled for use at designated times. An inventory log of when and how much treatment fluids used will be kept and updated after each participant treatment.
- 4.3. Biosafety: *N/A*
- 4.4. Stem Cells: *N/A*

#### **5. Procedures Involved**

- 5.1. Study Design: Patients will be asked to indicate their peak pain level in the twenty-four hours prior to the appointment using a numeric rating scale (NRS). The NRS scale will consist of a 100mm line where 0 equals 'no pain' and 100 equals the 'worst pain imaginable'. Patients will be divided into one of two treatment groups, either standard cleaning protocol or Gentlewave irrigation. Patient demographics, anesthesia, cleaning and shaping instruments, irrigation technique, and obturation method and material will be recorded, along with extent of treatment rendered, and the occurrence of over-instrumentation or overfill of obturation material.

Following the first appointment, patients will be given the same NRS assessment to take home and asked to record their level of pain at 6, 24, 72, and 168 hours post-treatment.

### 5.2. Study Procedures:

- Procedures that will be performed regardless of whether research were being conducted include diagnostic examination and radiographic examination/interpretation. Diagnostic examination includes sensibility testing of the tooth/teeth in question, determination of whether or not a crack, fracture, or non-endodontic pathology exists, and determination of the etiology of endodontic pathology. Diagnostic exam procedures include thermal testing using either Endo Ice Refrigerant spray or heated gutta-percha, electric pulp testing device if thermal testing is inconclusive, percussion testing using the handle of a mouth mirror and digital palpation of gingival area near the tooth/ teeth in question. Periodontal examination will also be performed for probing depths and mobility. Transillumination and methylene blue staining may be performed if a crack or fracture is suspected. Radiographic examination includes at least two periapical radiographs for posterior teeth and one periapical radiograph for anterior teeth. A limited field of view CBCT may be taken if necessary.
- Confirmation of pre-operative pain (symptomatic status) will be determined by having the patient record their pain level to percussion at the initial examination using the NRS scale. Additionally, the force required to cause pre-operative pain to biting will be recorded using a digital occlusal force meter.
- During the treatment portion of research, the tooth needing treatment will be sufficiently anesthetized with local anesthetic to undergo the procedure pain-free. A rubber dam will be placed isolating the tooth in question and one tooth adjacent to that tooth both mesially and distally. The pulp chamber will be accessed and prepared for straight line access to all canal orifices. During access, all caries and defective restorations will be removed. If there is a defective crown, it will be removed prior to rubber dam isolation. Hand files and electronic apex locators will be used to determine the working length of each files. Working length will be verified using a periapical radiograph. At this point is where the two treatment groups will diverge.
- For the standard protocol (control) group, following working length determination, all canals will be cleaned and shaped using rotary files to at least a size 20.04 canal size and to within 0.5 to 1 mm short of the apical terminus. Appropriate final canal size will be determined by the clinician treating the patient. Between each file, 5.25% NaOCl will be

used to disinfect and wash the canals of debris. After the canal has been cleaned and shaped to 20.04, sodium hypochlorite will be passively activated using an ultrasonic instrument for 30 seconds per canal. Next, each canal will soak in 17% EDTA for 1 minute, will be rinsed in 5.25% NaOCl, and finally undergo a final rinse of 95% ethanol. Canals will be filled with Ca(OH)2 and a temporary restoration will be placed with a cotton pellet and restorative material of the clinician's choice. All of these steps make up our standard protocol and would be performed whether research is being conducted or not.

- For the Gentlewave treatment group, the standard protocol will be followed until working lengths are determined. Each canal will be shaped to a canal size of 20.04 or 20.06 and to 1mm short of the apical terminus. An occlusal platform will be prepared to allow Gentlewave treatment of the tooth using the Kool-dam material recommended by Sonendo. The Gentlewave system will be held on the tooth by the clinician and will cycle through five minutes of 3% sodium hypochlorite, two minutes of 8% EDTA, and a final rinse of distilled water. Canals will be filled with Ca(OH)2 and a temporary restoration will be placed with a cotton pellet and restorative material of the clinician's choice. If the research were not conducted, these patients would be treated using the standard protocol as above.
- Pain Management: As both arms include standard of care treatment, pain management will be the same recommendation as our standard, non-research related treatment. Recommendations for pain management include: 600mg Ibuprofen every 6 hours for pain. If additional pain relief is needed, patients are instructed to add 500-650mg Acetaminophen every 6 hours. If these medicines are necessary, participants will be instructed to record which medicines were taken, the amount, at which times, and how often. This will be returned along with the NRS pain assessment.
- Following the first and final appointment, regardless of procedure, participants will be given the same NRS pain assessment from pretreatment to take home and asked to record their level of pain at 6, 24, 72, and 168 hours post-treatment. Participants will be given an envelope with prepaid postage to return the pain assessment form to the graduate endodontics office.
- Should a participant's pain assessment form not be returned, a phone call will be placed to remind the participant to return the form.

- The Gentlewave system is a FDA cleared root canal irrigation device that is used to remove necrotic tissue, debris, biofilm, and bacteria while leaving dentin intact and preserving tooth structure. The Gentlewave irrigation replaces the NaOCl ultrasonic activation and EDTA steps of the standard protocol.
- The data to be collected include patient demographics, pretreatment/posttreatment NRS pain assessment recordings, anesthetic technique/amount, cleaning and shaping instruments, irrigation technique (standard vs Gentlewave), and obturation method/material will be recorded. The occurrence of over-instrumentation or overfill of obturation material will also be recorded.
- The total time commitment for all participants, regardless of arm assignment, will 4+ hours of treatment time and 5 minutes a day for 14 days to record pain levels.

5.3. Study Duration:

- The anticipated duration for enrolled participants is the amount of time to complete treatment (multiple visit treatment) and the 14 days (7 days after 1st visit and 7 days after final visit) following treatment during self-evaluation of post-operative pain.
- The anticipated time to complete all study procedures, follow-up, and data analysis is projected to be 12-15 months.

5.4. Individually Identifiable Health Information: The study will involve access to individually identifiable health information. The purpose of access is to ensure patients are treated safely and are not administered any medication/anesthetic the patient may be allergic to or that may be contraindicated for use with any medication they may be currently taking.

5.5. Use of radiation: The study will involve the use of radiation in the completion of endodontic treatment. This involves taking multiple periapical radiographs and possibly limited field of view cone beam computed tomography.

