accessing the pulp chamber, all caries, defective restorations, and deficient crowns were removed. A pre-endodontic build-up was placed if necessary, to maintain isolation. Straight-line access to the pulp orifices was then achieved. Hand files and an electric apex locator were used to determine the working length which was then verified with a periapical radiograph.

For the control (standard endodontic treatment) group, during the initial appointment the following were accomplished: Clinical exam, pre-endodontic build-up (if necessary), working length determination, all canals were instrumented using hand and rotary files to a minimum size and taper of at least 25/04 to within  $\frac{1}{2}$  to 1 mm short of the apical terminus. Between each file, 5.25% NaOCl was used to disinfect the canals and flush debris. Following instrumentation, NaOCl was ultrasonically activated for 30 seconds in each canal. Canals were then dried; UltraCal XS (Ultradent Products, Inc., South Jordan, UT) was placed into each canal measured 2mm short of working length. A spacer of either sterile cotton pellet or sterile sponge were placed followed by an interim restoration of either Cavit or Glass ionomer to a minimum thickness of 3.5mm.

In the experimental group during the initial appointment the following were accomplished: Clinical exam, pre-endodontic build-up (if necessary), working length determination, all canals were instrumented using hand and rotary files to a maximum size and taper of 20/07 to 1 mm short of the apical terminus. Between each file, 5.25% NaOCl was used to disinfect the canals and flush debris. Following instrumentation of the canals, Kool-dam heatless liquid dam was used to build an occlusal platform that functioned to support the GWS handpiece and seal the access opening during treatment. For molars, included gauges were used to determine the proper handpiece attachment. The GWS handpiece was positioned on the tooth for the entirety of the GWS treatment, which varied in length of time depending on the pulpal diagnosis of the tooth. The canals were then dried using paper points and UltraCal XS (Ultradent Products, Inc., South

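### The NRS models pool necrotic and vital teeth without a diagnosis term, and the SAP's visit-1 arms differ in more than irrigation, so the conclusion should be limited to the regimens as described

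*Protocol*

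**What the plan says.** **Diagnosis.** Protocol 2.3 cites a cohort study in which pain after treatment was more frequent and more severe in vital than in non-vital teeth. The Protocol's Study Summary (sample size row) and 10.1 plan necrotic and vital symptomatic teeth as two subcategories. The SAP's inclusion criteria admit necrotic pulp and both forms of irreversible pulpitis. The SAP's Statistical Method fits one linear mixed model to NRS scores and one logistic mixed model to NRS categories. Each has arm, time, their interaction, the pre-operative score or category, and a participant effect. Pulpal diagnosis appears only in a chi-square comparison of the arms.

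**Visit-1 regimens.** In Protocol 5.2, after ultrasonic activation of NaOCl in the control arm, "each canal will soak in 17% EDTA for 1 minute". A 5.25% NaOCl rinse and 95% ethanol follow, then calcium hydroxide. The paragraph ends: "All of these steps make up our standard protocol and would be performed whether research is being conducted or not". Control canals are "cleaned and shaped using rotary files to at least a size 20.04 canal size", with the final size left to the clinician. For Gentlewave, "Each canal will be shaped to a canal size of 20.04 or 20.06 and to 1mm short of the apical terminus", and the device "will cycle through five minutes of 3% sodium hypochlorite, two minutes of 8% EDTA, and a final rinse of distilled water".

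The SAP's treatment description (under its Exclusion criteria heading) opens "For the control (standard endodontic treatment) group, during the initial appointment" and goes from activated NaOCl to drying and dressing. Control canals are prepared with "hand and rotary files to a minimum size and taper of at least 25/04", Gentlewave canals with "hand and rotary files to a maximum size and taper of 20/07". EDTA, the NaOCl rinse and ethanol appear at the second appointment, with no distinction by arm. The SAP describes the take-home 6-168 h form only after the first appointment. Its Research Design section gives the two irrigation methods as the independent variables.

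**The concern.** There are two separate issues.

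First, the plan leaves a factor that its own background calls prognostic out of both outcome models, although it is collected. Comparing the arms on diagnosis by chi-square describes imbalance but does not correct for it. What is at stake is some precision, and a treatment estimate that carries any chance imbalance in vital teeth.

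Second, the SAP calls its control standard and attributes the contrast to irrigation. By its own description, the visit-1 control lacks three steps of the Protocol's standard sequence, and apical size also differs by rule. Visit 1 is the treatment that the SAP's 6-168 h form follows. What is at stake is what a difference may be credited to, and which comparator the reader believes was used.

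**Working it through.** **1. Regimens side by side (visit 1)**

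| Feature | Protocol 5.2 | SAP |
|---|---|---|
| Control steps after activated NaOCl | 3 (EDTA, NaOCl rinse, ethanol) | 0; listed at visit 2 |
| Control size | at least 20.04, clinician decides | at least 25/04 |
| Gentlewave size | 20.04 or 20.06 | at most 20/07 |
| Smallest control v largest Gentlewave tip | 20 v 20 | 25 v 20 |
| Gentlewave NaOCl + EDTA time | 5 + 2 = 7 min | varies by diagnosis, times not given |

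The Protocol permitted a size difference; the SAP makes one unavoidable at the tip. Assuming that size is tip diameter in 0.01 mm and taper is mm per mm, 20/07 becomes wider than 25/04 beyond (0.25 - 0.20)/(0.07 - 0.04) = 1.67 mm from the tip. The difference is therefore apical, not overall. The effect of any of these features on NRS cannot be derived from the documents.

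**2. The plan's own sample size.** Protocol 15.2: 17 per group, 80% power, 1 SD. Two-sample t test, two-sided 0.05 (sidedness assumed), noncentrality √(17/2) = 2.92, 32 df: power 80.7%. This reproduces. The SAP's 19 per arm has no stated effect size; at 1 SD it gives 85.1%.

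**3. Chance imbalance in diagnosis.** Assumptions: 19 per arm, allocation not stratified by diagnosis (not stated), vital share 30-70%. With X and Y independent Binomial(19, p), P(|X - Y| ≥ 4) is 21.4% at p = 0.3 or 0.7 and 25.6% at p = 0.5.

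**4. Shift and precision in the linear model.** Assumptions: vital-necrotic difference d of 10-20 points, SD s of 20-30, baseline NRS explaining nothing.
- Shift from a 4-tooth imbalance: (4/19) × d = 2.1 to 4.2 points.
- Standard error of the contrast: s√(2/19) = 6.5 (s = 20) or 9.7 (s = 30), so the shift is 0.22 to 0.65 standard errors.
- Variance share of diagnosis at an even split: 0.25 d²/s². The standard error is multiplied by √(1 - 0.25 d²/s²), then by √(35/34) = 1.015 for the extra coefficient at N = 38.

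| d, s | Gross reduction | Net reduction |
|---|---|---|
| 10, 30 | 1.4% | 0.0% |
| 10, 20 | 3.2% | 1.8% |
| 20, 30 | 5.7% | 4.3% |
| 20, 20 | 13.4% | 12.1% |

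At a 30% or 70% vital share, 0.21 replaces 0.25 and the net range is about 0-10%.

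**5. Dependence on enrolment.** The SAP gives 38 as the number needed, not as the number enrolled. The Protocol's Study Summary plans 50 in each diagnostic category, 100 new patients; 10.1 requests about 150. At an assumed 50 per arm, a proportionally similar imbalance (11 or more, since 50 × 4/19 = 10.5) has a 2.2-3.5% chance. Power at 1 SD for separate necrotic and vital analyses is 51-56% with 9-10 per arm per category (38 patients, even split) and 93% with 25 (100 patients).

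**6. The logistic model.** The percentages in step 4 are for a linear model and do not carry over.

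**The case against.** **Much of the regimen detail is already disclosed.** The SAP states canal sizes and between-file irrigation openly by arm. That stands: copying them elsewhere would be editorial. What is left is the claim that irrigation is the only difference, the label standard, and the scope of the conclusion.

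**The figures lean on 38 as enrolment and give baseline NRS no role.** Both points stand. If vital and necrotic teeth differ in pre-operative pain, the planned baseline term already removes part of any imbalance. A reader might also infer that the Protocol's separate necrotic and vital analyses had become unworkable. That holds only if 38 is the enrolled number, which the documents do not say.

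**Apical size could already differ.** True. Protocol 5.2 let clinicians enlarge control canals without limit. Only the guarantee of non-overlap is new.

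**Silence may not mean omission.** The SAP does not name the Gentlewave fluids either, yet nobody would conclude that none were used. For the control arm, placing EDTA explicitly at visit 2 makes omission at visit 1 the natural reading, but it remains a reading. A reader might infer that controls never received these steps; the SAP lists them at visit 2.

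**No bias is shown.** Correct. The documents describe a randomised comparison, and neither the missing covariate nor the changed regimen biases the contrast of the regimens as delivered.

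**Conclusion.** The point holds in a limited form and is worth considering, not essential.

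Both NRS models omit a factor that the Protocol calls prognostic and planned to separate. Adding it costs almost nothing. The gain is modest: about 0-12% off the standard error net, with a 21-26% chance of an imbalance of four or more teeth. Both figures assume 19 per arm; the first also ignores baseline NRS and assumes an even split, a 10-20 point difference and an SD of 20-30; the second assumes unstratified allocation and a 30-70% vital share. With larger enrolment the imbalance risk falls sharply.

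As the SAP is written, the 6-168 h contrast compares the Gentlewave regimen at a smaller apical size with activated NaOCl at a larger apical size and no visit-1 EDTA. It does not compare Gentlewave with the Protocol's standard sequence, and a difference cannot be credited to irrigation alone. How far this matters for NRS cannot be quantified. A reader might go further and treat the unstated Gentlewave cycle times as a flaw in the comparison. They are a reporting detail only.

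**What to change.** 1. **Models.** Add pulpal diagnosis as a fixed effect (necrotic v vital, taking symptomatic and asymptomatic irreversible pulpitis as vital; 1 df) to both the linear and the logistic NRS model. The logistic model matters because the Protocol's primary outcome is occurrence of pain. The SAP is written in the past tense. If analyses are complete, keep the planned models and report these beside them as a labelled adjusted analysis. State that necrotic and vital teeth are pooled, unlike Protocol 10.1.

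2. **Comparator and conclusion.** In the SAP's Research Design section, stop naming irrigation as the only difference and note the departure from Protocol 5.2. Limit the 6-168 h conclusion to the Gentlewave regimen with smaller apical size versus activated NaOCl with larger apical size and no visit-1 EDTA. If treatment notes show that controls did receive EDTA at visit 1, correct the SAP's treatment description instead.

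Give the Gentlewave cycle times by diagnosis if they were recorded.

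Cost: one covariate already collected, one coefficient per model, one rewritten paragraph and a check of treatment notes. No new patient data.
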